### 8.2 Data Quality Assurance

August 13, 2024 Version #7

As stated in Section 7.6:

#### **Data Collection Forms**

Continuous glucose monitoring data will be monitored every 2 weeks through the Dexcom application programing interface, and mobile diaries will be monitored daily through the GlucoseZone application programming interface. This monitoring will include audits for completeness. Other biosensors that continuously sync with their web application programming interface (Fitbit, insulin devices) will be monitored every 2 weeks through the relevant application programming interface. Actigraph hip watch data will be audited for completeness when the device is downloaded after each 2-week assessment period. [name] will also perform quarterly audits for conformance with source document completion.

# Data Integrity and Protection of Databases

Databases will be exported quarterly from REDCap onto Yale University secure servers and audited for completeness and aberrant values using frequency statistics. Datasets from biosensors will be checked in on REDCap checklists as they are downloaded, and the checklists will be audited quarterly. Original reports of all biosensor downloads will be retained for verification and further data analysis.

#### 8.3 Data or Specimen Storage/Security

For data storage and security, REDCap and Yale OneDrive are password-protected and only members of the research team will be given authorized access by the PI. All research team members will complete standard IRB trainings in protection of human subjects before being added to the protocol. All data is coded by anonymous study ID number which is linked in one section of the REDCap database to identifiers.

#### 8.4 Study Records

Study records will be maintained by the PI and accessed by research staff on a Yale OneDrive folder. These include all IRB documents maintained on Yale OneDrive and IRES, an internal standard operating procedure manual, AE forms that follow a standard departmental template containing the items detailed in section 6.3, and confidential data sources (listed in section 8.1 paragraphs 3-4 and below in section 8.5). In addition, e-Consent forms are stored on REDCap and can be exported as pdfs for audits when necessary.

#### 8.5 Access to Source

#### As stated in section 8.1:

Participant confidentiality and privacy is strictly held in confidence by the participating investigators, their staff, and the sponsor(s)/funding agency. Therefore, the study protocol, documentation, data, and all other information generated will be held in strict confidence. While there is a possibility of a security breach compromising subject confidentiality, several steps will be taken to safeguard the confidentiality of subjects and their data as detailed below.

All research activities will be conducted in as private a setting as possible.

All research data collected outside of the mobile applications will be assigned a study participant number and that number will only identify participants in digital databases on REDCap or Actigraph Actilife. Audio-recorded interviews and orientation sessions will be transcribed and names, places, and any other identifying information will be removed. Recordings will then be promptly destroyed. The names of participants will not be associated with these data and assessments and transcriptions will be maintained according to participant study number. A master list connecting participant study numbers to participant names will be kept on a secure server where it can only be accessed by senior level project staff. Any information published as a result of the study will be such that it will not permit identification of any participant.

All research data that is collected via the mobile applications (CGM, diary/survey responses, exercise performance, insulin usage, carbohydrates, GPS) will be stored on the relevant web application programming interface (API) platforms (Dexcom, Fitbit, GlucoseZone), researcher dashboard (Keto-Mojo, Ilumivu, Qualtrics), or user dashboard (InPen) in accord with Yale Information Technology Services protocols (Sect 2.2, Table A1). After syncing the data, the data will be immediately deleted from the participants' biosensor devices and smartphones. Web-based application and user sessions are encrypted between the server and client browser through the use of industry standard SSL certificates. As soon as each participant completes the study protocol, their data will be immediately transferred from the API platform to Yale secure servers by secure file-protection strategies, assigned to the de-identified

August 13, 2024 Version #7

participant study number noted in the previous paragraph, and deleted from the API platform. All data is encrypted both at rest and in transit.

Yale Information Technology Services has reviewed all devices that transmit data for the study. They have determined that the Actigraph GT9X blinded watch, Dexcom G6 CGM, Fitbit Inspire 3 smartwatch, Ilumivu Mobile Surveys, Qualtrics Mobile Surveys, InPen, and participants' own insulin pumps will not collect or transmit any HIPAA-covered health information for study purposes. They have determined that GlucoseZone in this study will collect and transmit HIPAA-covered health information, in a manner meeting the HIPAA privacy and institutional standards, including GlucoseZone's specific data use agreement with Yale University.

Right to privacy for participation in this research will be protected through alphanumeric coding of data (in place of names) and proper storage of research records, including interview transcripts and data downloaded from the web API platforms. Collected materials will be maintained via an alphanumeric reference system maintained by [name]. Participants' names will appear only on the consent form, the HIPAA authorization form, and a master list maintained on REDCap that is separate from research data. Our data collection and management procedures are fully compliant with HIPAA. Access will be limited to personnel intimately involved in the study. Electronic data will be deidentified and password protected. Only members of the study team will have access to the physical or electronic data.

Study participant research data, which is for purposes of statistical analysis and scientific reporting, will be transmitted to and stored in a password-protected OneDrive folder at the Yale School of Medicine Section of General Internal Medicine. This will not include the participant's contact or identifying information. Rather, individual participants and their research data will be identified by a unique study identification number. The study data entry and study management systems used will be secured and password protected. At the end of the study, all study databases will be de-identified and archived indefinitely at the Yale School of Medicine Section of General Internal Medicine.

Data availability: Individual deidentified participant data (including data dictionaries) will be shared. This includes individual participant data that underlie the results reported in any aspect of a published article (text, tables, figures, and appendices). Other documents that will be available include the study protocol, statistical analysis plan, informed consent form, and analytic code. The data will be available immediately following publication with no end date. Data will be shared with researchers who provide a methodologically sound proposal to achieve aims in the approved proposal. Proposals should be directed to [name] at Yale University ([contact]). To gain access, data requesters will need to sign a data access agreement. Data will also be uploaded to NIH per the NIH data sharing agreement.

Representatives of the Institutional Review Board (IRB), regulatory agencies or study sponsor/funding agency may inspect all documents and records required to be maintained by the investigator for the participants in this study. The study site will permit access to such records.

#### 8.6 Retention of Records

Identifiers and consent forms will be retained on REDCap for 3 years following the completion of live data collection and anonymous data will be retained indefinitely.

August 13, 2024 Version #7

# 8.7 Data and Safety Monitoring Plan

#### I. OVERVIEW

This clinical study is a feasibility study of the alpha version of an informatics-based digital application to promote safe exercise.

The Data and Safety Monitoring Plan (DSMP) outlined below for the study will adhere to the protocol approved by the Yale University IRB.

#### **II. ADVERSE EVENTS**

#### A. Adverse event assessment

The expected risks of this protocol are:

**Confidentiality:** Due to the collection of private identifiable information, there is a possibility of a security breach compromising subject confidentiality.

**Hypoglycemia:** There is risk of hypoglycemia due to exercise.

**Hyperglycemia:** There is a risk of hyperglycemia due to exercise. Hyperglycemia can lead to diabetic ketoacidosis.

**Exercise-related injuries:** Exercise may cause muscle soreness/pain, muscle strain, cardiovascular events, and tiredness during or after the activity.

**Study questionnaires and interviews:** Participants may experience some distress when discussing factors important to diabetes, diabetes management, and psychosocial stressors.

**Continuous glucose monitoring (CGM):** Participants will use Food and Drug Administration (FDA) approved Dexcom G6 CGM as part of the American Diabetes Association standard of care. There is a low risk of developing a local skin infection at the site of the sensor needle placement. Itchiness, redness, mild bleeding, and or bruising may occur at the insertion site. Participants may develop localized reactions to adhesive used to secure the sensor.

**Fitbit:** In a very small number of participants (~3% in a recent report) the Fitbit may contribute to skin irritation or allergies.

The approved protocol and consent form will address these risks.

August 13, 2024 Version #7

# **Tracking**

A. Daily monitoring during first 2 weeks for ketoacidosis, severe hypoglycemia, and other health risks associated with exercise:

We will detect any diabetic ketoacidosis or severe hypoglycemia within 24hr and suspend exercise until a personalized preventive strategy can be formed. To achieve this level of monitoring, a research assistant will monitor daily the biometric dashboard which contains Bluetooth-captured glucose, ketones, and exercise start/stop times. Safety signals include any of the following during or within 1hr of exercise: 1) Diabetic ketoacidosis (glucose ≥270 mg/dL + ketones ≥1.0 mmol/L), 2) Possible diabetic ketoacidosis (glucose ≥270 mg/dL and failure to test ketones), and 3) Possible severe hypoglycemia (glucose <55 mg/dL). Research staff will respond to each of these events within 24hr of its occurrence by informing the participant to immediately suspend the exercise program (app account will be suspended) until the participant has been contacted by a study physician. The physician will alert the participant and the participant's primary diabetes care provider to the issue and develop a prevention strategy, consulting with the primary diabetes care provider as needed. The exercise suspension will then be lifted, unless the participant has met the protocol's stoppage criteria (>1 episode of severe hypoglycemia, 1 episode of diabetic ketoacidosis not closely related to pump site failure).

In the event of the "possible" occurrences (#2, #3), physician contact can be replaced initially by research assistant contact to query symptoms. Then, if possible diabetic ketoacidosis is supported by the participant reporting symptoms, or possible severe hypoglycemia is supported by the participant reporting altered mental and/or physical status requiring assistance from another person for recovery, physician contact will be required as in paragraph #1 above.

We will detect any other exercise-associated health risks within 24-36hr and suspend exercise until a personalized preventive strategy can be formed. To achieve this level of monitoring, the morning survey question about prior day's clinical events (Appendix 8a, last question) will be asked of participants and monitored by research staff daily. If the participant reports a clinical event, the PI will complete Adverse Event review and summary (c.f. Protocol Sect 6.3) the same day (i.e., within 24-36hr of the reported event). If the event may be exercise-related, the participant will be informed to immediately suspend the exercise program (app account will be suspended) until the participant has been contacted by a study physician. The physician will alert the participant to the issue and develop a prevention strategy, consulting with the participant's primary diabetes care provider as needed. The exercise suspension will then be lifted, unless the participant has met the protocol's stoppage criteria.

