# Physical activity with T1D has been linked to glycemic destabilization and fear of hypoglycemia.

Lack of engagement in physical activity stems from the unique challenges of physical activity with T1D. Physical activity with T1D can dysregulate blood glucose, leading to hypo- and/or hyperglycemia during and up to 24hr later due to consumption of energy, increased insulin sensitivity, release of counterregulatory hormones, and various combinations thereof. The direction and magnitude of these glycemic fluctuations vary according to type of physical activity, personal insulin sensitivity, insulin-on-board, and hormone concentrations. There is also high interindividual variation in these responses due to factors not well understood. Predicting these fluctuations to adjust diet and insulin is challenging.

When these fluctuations bring blood glucose into clinically unsafe ranges, symptoms can require halting of physical activity. As well, a context where these symptoms are likely (e.g., downward-trending blood glucose or high insulin-on-board) can preclude the start of physical activity. Furthermore, repeated exposure to these symptoms leads to *fear of hypoglycemia*, the most reported barrier to physical activity among people with T1D. This fear can motivate people with T1D to avoid physical activity due to remembering past symptoms and anticipating future occurrence of symptoms.

This investigation does not address exercise for type 2 diabetes (T2D) which faces different barriers compared to T1D. There is less risk of hypoglycemia due to the nature of the medication treatment, and therefore less fear of hypoglycemia. Meanwhile there is greater associated stigma, since the disease has etiology rooted in modifiable lifestyle behaviors. In addition, obesity as a comorbidity is more common and more severe. Therefore there is greater relevance of obesity-related barriers such as joint pain, exercise equipment being too small, and weight stigma.

August 13, 2024 Version #7

[figure not shown]

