They will also be provided a comprehensive exercise safety orientation which is detailed in Appendix 22a. Briefly, the information includes review of devices, supplies, space, safe glucose ranges and carbohydrate snacking for exercise, reminders from CGM training pertinent to exercise, insulin adjustments around exercise, watching for symptoms, and who to call with concerns. They will be provided and instructed to keep carbohydrate-containing foods and drinks (eg, orange juice, glucose tablets) available to use when indicated by glucose testing or symptoms. In addition, they will be educated regarding the American Diabetes Association guidelines for self-monitoring blood glucose and urine ketones, if indicated, and appropriate adjustments of diet and insulin before, during, and after engaging in exercise. For instance, if blood glucose is less than 90 mg/dL, they can consume 10-20g of fast-acting carbohydrates (eg, 4 oz of orange juice or 3 glucose tablets) and wait to commence with exercise until blood glucose is confirmed to be above 90 mg/dL. If blood glucose is greater

Protocol Number 2000035846

August 13, 2024 Version #7

than 270 mg/dL and not associated with a recent meal, they must check their blood for ketones and avoid exercise if they have ketones ≥1.0 mmol/L.

Participants will be encouraged to be vigilant for symptoms of hypoglycemia during exercise and for the remainder of the day because exercise increases the risk for nocturnal hypoglycemia. The symptoms they will be encouraged to be vigilant for include cold, clammy skin, pallor, difficulty concentrating, shakiness, lack of coordination, irritability, hostility, and poor behavior, a staggering gait, fatigue, nervousness, excessive hunger, headache, blurred vision and dizziness, and abdominal pain or nausea. In these instances, they will be advised to refrain from exercise while checking blood glucose.

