Participants will be monitored for exercise-associated events (hypo- and hyperglycemia, diabetic ketoacidosis, other health risks) as detailed in the Data and Safety Monitoring Plan (Sect 8.7). In brief, a research staff member will daily review each participant's CGM data, fingerstick glucose tests, ketone tests, exercise start times, and diary records of hypoglycemia and other clinical events (see Data and Safety Monitoring Plan "Tracking" section) each of the first 14 days of the trial for each participant. Instances of severe hypoglycemia, diabetic ketoacidosis, a missed ketone test, or other clinical event will result in immediate discontinuation of exercise until a physician has alerted the participant and the participant's primary diabetes care provider to the issue and developed a prevention strategy, consulting with the primary diabetes care provider as needed. For instances of a missed test, physician contact can be replaced initially by research assistant contact to query symptoms and troubleshoot testing procedures, followed by physician contact if symptoms were present.

The principal investigator [name] and a study physician (Drs. [name] or [name]) will review the above data plus carbohydrate and insulin dosing around exercise, every 2 weeks during the clinical trial. Participants exhibiting patterns confirmed by the physician to be indicative of problematic exercise-induced hypo- or hyperglycemia will be alerted to the issue and referred to their diabetes care provider for follow-up (all patients will submit provider information to the study team at study start). [name] will join at least every other occurrence of these meetings (i.e., at least every 4 weeks) and provide a second review of [name] medical management decisions. Participants will be trained in allowing their provider to access their CGM data. Mild hypoglycemia will not be exclusionary since such individuals are in high need of exercise intervention. Any day-to-day decisions about clinical care, including adjustment of insulin dosing or CGM target ranges will be made by the participant's provider, not the study physicians. Clinical providers will not monitor CGM in real-time.

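### Tracking A promises to detect any ketoacidosis or severe hypoglycemia within 24 hours, but its sensor signals stop 1 hour after exercise, and later events rest mainly on next-morning self-report

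*Combined protocol and SAP*

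**What the plan says.** Section 8.7, Tracking A, is headed "Daily monitoring during first 2 weeks for ketoacidosis, severe hypoglycemia, and other" health risks. It states: "We will detect any diabetic ketoacidosis or severe hypoglycemia within 24hr". The stated means is a research assistant's daily check of a dashboard holding glucose, ketones and exercise times. Then: "Safety signals include any of the following during or within 1hr of exercise". Three signals follow:

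- Signal 1: glucose of at least 270 mg/dL with ketones of at least 1.0 mmol/L.
- Signal 2: glucose of at least 270 mg/dL with no ketone test.
- Signal 3: glucose below 55 mg/dL.

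The response is to suspend exercise and the app account until a physician makes contact. For signals 2 and 3, "physician contact can be replaced initially by research assistant contact to query symptoms".

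The protocol describes a longer risk period. Section 1.1 speaks of exercise "leading to hypo- and/or hyperglycemia during and up to 24hr later due to consumption of energy". Section 2.2 asks participants to watch for symptoms "for the remainder of the day because exercise increases the risk for nocturnal hypoglycemia".

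Section 2.2 also describes a daily staff review of glucose, ketone and diary data for "each of the first 14 days of the trial for each participant". Its action rule is: "Instances of severe hypoglycemia, diabetic ketoacidosis, a missed ketone test, or other clinical event will result in immediate discontinuation of exercise". That rule has no time window.

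**The concern.** The promise covers any event, but the sensor mechanism offered to deliver it ends an hour after exercise. The protocol regards the following night as a time of raised risk.

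A reading below 55 mg/dL is not itself severe hypoglycemia, which section 2.2 defines by symptoms needing outside help. A glucose trace cannot show that. Tracking A handles this sensibly by using the reading as a reason to ask. The same reading at night gives staff no stated reason to ask, although they already review it. If the participant also does not report the event, exercise could continue before anyone on the study team enquires.

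**Working it through.** The plan gives no figure to reproduce. The check compares the text of the sections and then sizes the gap.

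**1. Share of time with a sensor signal.** Inputs: the 150 minutes per week target (6.1.1, Visit 4) and exercise on 5 to 7 days (Tool #2 sets at least 5).
- Hours covered = 2.5 + 1 per exercise day: 7.5 h for 5 days, 9.5 h for 7 days.
- Out of 168 h: 4.5% to 5.7% of the week.
- Of the 24 post-exercise hours named in section 1.1, 1 is covered and 23 (95.8%) are not.

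**2. What covers the other 23 hours.**

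| Route | Where | Limit |
|---|---|---|
| Morning question on prior-day hypoglycemia | 6.1.1, Visits 2 and 4; diaries monitored daily (2.2, 7.6) | Self-report |
| Clinical-events question | Daily in 8.7 Tracking A; daily for 2 weeks from visit 2, then every 2 weeks in 6.1.1 Visit 2; every 2 weeks only in 6.1.1 Visit 4 | Self-report; frequency inconsistent |
| Calls to the investigator or care team | 2.2, 8.7 | Self-report |
| Daily data review | 2.2 | Acts on named events and a missed ketone test; no glucose value for later readings |
| Weekly app report on nocturnal lows | 6.1.1, Tool #3 | Goes to participants |
| Weekly visit; two-weekly review | Table 1; 8.7 Tracking B | Too slow for 24 hours |

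The value above 500 mg/dL in section 2.2 defines severe hyperglycemia. It is not set as a dashboard trigger.

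**3. How often the morning route is missed.** The earlier pilot (1.2.1) had median diary completion of 98%, lower quartile 88%. Over 14 days:
- 14 × 0.02 = 0.28 missed mornings at the median.
- 14 × 0.12 = 1.7 at the lower quartile.

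This measures completion, not whether the answers were right.

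**4. Delay when that route fails.** The next staff step is up to 7 days (168 h) or 14 days (336 h) away. Session rates are 2.4 per week (pilot) and 5 per week (goal).
- Before the weekly visit: 2.4 to 5 sessions.
- Before the two-weekly review: 2 × 2.4 = 4.8 to 2 × 5 = 10 sessions.

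**5. Query load of a 24-hour window.** Assume 2-20% of post-exercise periods contain a later reading below 55 mg/dL. The documents give no rate, so this range is an assumption.
- Per participant over 2 weeks: 4.8 × 0.02 = 0.10 to 10 × 0.20 = 2.0.
- For 11 active participants (the Tracking B maximum), all in the daily-check period at once: 11 × 4.8 × 0.02 = 1.1 to 11 × 10 × 0.20 = 22.
- For all 24: 24 × 4.8 × 0.02 = 2.3 to 24 × 10 × 0.20 = 48. With every period flagged, the ceiling is 115 to 240.
- Time inside the look-back, for 15-40 minute sessions (2.2) on separate days: 4.8 × 24.25 / 336 = 34.6% to 10 × 24.67 / 336 = 73.4%.

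**6. Which 2 weeks.** Section 2.2 counts from the start of the trial. Fourteen days from visit 1 (Day 1) end on Day 14, and from visit 2 (Day 8) on Day 21. App exercise starts at visit 4 (Day 22). On either count the daily check would end first, on the nominal schedule.

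**The case against.** The strongest reply is that every participant is asked about prior-day hypoglycemia each morning, whatever the sensor shows, and that staff look at the answers daily. Severe hypoglycemia by definition involves another person, which makes a report more likely. A sensor-prompted query also ends in self-report, so it helps only those who miss or misanswer the morning item but would tell an assistant. All of this stands, and it is why the point is minor.

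Three further replies stand in part.

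- The word introducing the signals may not be exhaustive, and monitoring details may sit in Appendix 22b or a procedure manual. Neither is available, and no later glucose trigger for staff appears in the text, so the possibility does not close the gap.
- A missed ketone test is an action trigger in section 2.2 without a time window. But the rule that calls for the test is tied to starting exercise, so it does not reach an overnight low.
- Suspending the app for every late low would be costly and would affect video use, a feasibility measure. That is a fair limit on the remedy, and the change below respects it.

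A reader might infer that overnight events go unnoticed for 7 to 14 days as a rule. The documents do not support that. The delay arises only when the morning report fails. Nor do they support reading the start-of-trial wording as leaving exercise unmonitored: Tool #2 has staff monitoring the dashboard daily for exercise safety during the intervention.

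**Conclusion.** The mismatch is real and minor. The 24-hour promise is broader than the listed signals, and after the first hour it holds only as far as participants report or the reviewer happens to recognise an event. The affected group is those who miss or misanswer the next morning's question during the daily-check period.

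The number of missed events cannot be computed, because no rate of low readings is given. Four earlier trials using these procedures had no severe hypoglycemia or DKA (2.2), so nothing here suggests that many events would be missed. The conclusion rests on the available text. The query load rests on the assumed 2-20% range.

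**What to change.** In Tracking A, during the daily-check period:

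- Apply signals 1 and 3 up to 24 hours after exercise, including overnight. Keep signal 2 at 1 hour, because ketone testing is asked for only when a high reading is not meal-related.
- Let a late reading below 55 mg/dL prompt only the assistant's symptom query. State that the app account is not suspended unless the participant confirms needing another person's help. Send a late signal 1 to the study physician.
- Reword the promise: sensor-flagged events in the stated window are acted on within 24 hours, and other events when self-reported. Later DKA without a ketone test would still depend on self-report.
- State that the 2 weeks of daily checks, and the daily clinical-events question, run from the start of app exercise (visit 4, Day 22). Align sections 2.2 and 6.1.1 with this.

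No new device or data stream is needed, since staff already review these data daily. The cost is the extra queries estimated above. Some will concern lows unrelated to exercise, because the look-back spans about 35-73% of the 2 weeks.
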